5.3. Long Term Follow up

Subjects who completed therapy, including treatment with or without retreatment, treatment with maintenance, or discontinued treatment for any reason other than clinical or radiological progression will enter the Long Term Follow up period. Subjects will be evaluated every 8 weeks for one year (until Amendment 5), and every 9 weeks (Amendment 6). During this Long Term Follow up Period, if a subject progresses or receives an intervening anti-cancer therapy, the subject will then enter the Survival Follow up Period.

Subjects who discontinue treatment due to clinical or radiological progression or Withdraw Consent from study treatment(s) will not enter Long Term Follow up, but will enter survival follow up as outlined below.

5.4. Survival Follow-up Period

Following completion of the treatment and long-term follow-up, as applicable, all subjects will be followed for survival. After that initial assessment of all study subjects, any surviving subjects will have their survival status assessed approximately every 3 months by either a telephone or in-person contact until study completion or termination by the Sponsor. With the exception of noting the first use of subsequent anti-cancer therapies, no other data (e.g., subsequent therapies, performance status etc.) beyond survival will be collected during these calls/visits.

5.5. Injection Procedure

For all injections, proper precautions to prevent bleeding will be followed per the institutional guidelines for anti-coagulants for this patient population. The risk of the procedure should be similar to a biopsy. Greater precautions should be taken when injecting deep tumors. Subjects cannot be on aspirin or NSAIA. Anticoagulants must be held with proper washout period prior to injection and not re initiated until the physician is confident that there have been no bleeding complications from the procedure.

Cohort A1, EA:

Superficial Tumors

The minimum tumor size must be \geq 1.0 cm in diameter on Day 0. An eligible superficial tumor is defined as one that has not been previously irradiated, and has had at least 4 weeks to heal after any surgery or open biopsy. Note superficial tumors that have been irradiated previously but have evidence of active tumor growth, can be considered.

Superficial tumor injection: A sentinel subject with accessible and eligible superficial tumors in the skin, subcutaneous tissues, and/or lymph nodes will receive up to 3 IT injections into different tumors that are considered the most **troublesome** (*defined as the largest that are without confounding factors to permit local toxicity assessment and*

which are causing the greatest morbidity (acknowledging that this is a subjective assessment). The largest tumor should be targeted first).

After IT injections, the sentinel subject was monitored for at least 6 hours post-injection with vital signs, physical exams including close examination of the injection site and surrounding tissues for any untoward reactions, safety labs, and adverse events (see [Table 11](#) for 28 day dosing and [Table 12](#) for 14 day dosing). If there were no safety concerns, the subject would have been discharged to return to the clinic on Day 1 for the same safety follow up as on Day 0. The subjects would have been admitted to the hospital for observation if deemed medically necessary. This subject would have returned for safety evaluations on Days 7 and 14. On Day 14 or day 28 (cohort dependent) the subject was evaluated for additional IT injections into superficial tumors. If the subject had no persistent adverse events greater than Grade 2 (NCI CTCAE v 4.03) that could reasonably be attributed to the IT injection or the components of INT230-6, the subject could have received repeat injections in up to 5 tumors on day 28, and on subsequent cycles any number tumors chosen by the investigator.

After this first subject completed at least 28 days of follow up without persistent \geq Grade 3 (NCI CTCAE v 4.03) adverse events that could reasonably be attributed to INT230-6, additional subjects were enrolled in this cohort.

Note: On subsequent cycles, previously injected or new tumors could have been treated. Data from animals suggest re-injecting the same tumors leads to better tumor control. Ultimately the decision to re-inject the same tumors was made by the treating physician. The total number of additional tumors that were readily injectable were considered. Ultrasound was used for needle placement to avoid injecting areas of necrosis.

Cohorts B1, EC, EC2, EC3, DEC, DEC2, FEC, GEC

All Tumor Types Including Deep Tumors

Subjects having previously identified deep tumors observed using ultrasound, CT scan, MRI or PET/CT technologies will be eligible for treatment of their deep tumors provided the inclusion and exclusion criteria are met. The procedure will be done with ultrasound- or CT scan-, directed IT injection into deep tumors of at least 1.0 cm in diameter. Most **troublesome tumors** are defined as the largest that are without confounding factors, such as an unclear window to approach the tumor, unclear path for the needle which avoids major structures, scarring, proximity to large vessels, large areas of necrosis, inability to ascertain a local toxicity assessment. Most troublesome tumors are causing the greatest morbidity (acknowledging that this is a subjective assessment). The technical feasibility will be assessed by an interventional radiologist during the screening process to determine if the subject can be treated with this approach and what the most suitable tumors are for injection. The largest tumor should be targeted first with the least amount of puncture wounds. Rex Medical deep tumor injection device (QuadraFuse) can be used to enable proper dispersion of the drug product throughout the different quadrants of

large tumors (device to be provided by the Sponsor). See [PK and Biomarker Manual](#) and [Injection Manual](#) for further information.

After IT injections, the sentinel subject in cohort B1 (any others are to be designated by the SSC) was monitored for at least 6 hours post-injection with vital signs, physical exams including close examination of the injection site and surrounding tissues for any untoward reactions, safety labs, and adverse events (see [Table 12](#)). If there were no safety concerns, the subject was discharged to return to the clinic on Day 1 for the same safety follow up as on Day 0. The subject would have been admitted to the hospital for observation if deemed medically necessary.

Subjects will return for safety evaluations on Days 7 and 14 for cohort B1 and weekly for all E cohorts. On Day 14 for all E cohorts, and Day 28 for cohort B1, subjects will be evaluated for additional IT injections. If the subjects have no persistent adverse events greater than Grade 2 (NCI CTCAE v 4.03) that can reasonably be attributed to the IT injection or the components of INT230-6, the subjects can receive repeat injections. Over the course of the induction phase, investigators should attempt, if safe, to dose as many tumors as possible at least 2 or 3 times at the proper dose as noted in [Table 8](#).

It is not necessary to inject each tumor on each of the 5 induction dosing sessions. For subjects who received 3 injections at the proper dose (from [Table 8](#)) in a given tumor prior to completion of 5 dosing sessions decisions regarding further treatment should be discussed with the Medical Monitor.

Note: On subsequent cycles, previously injected or new tumors may be treated. Data from animals suggest re-injecting the same tumors leads to better tumor control. The treating physician will ultimately decide which tumors will be injected, taking into consideration the response of the injected tumor(s) and the number of additional tumors that can be readily injected. Ultrasound or CT guidance may be used for needle placement to avoid injecting areas of necrosis.

Methodology:

INT230-6 will be injected into the periphery of the accessible and deep body tumors through the smallest and shortest gauge needle as possible to reach the entire depth of the tumor. For deep body tumors, ultrasonography or CT guidance at physician's choice will be used to place the needle into the tumor. The needle will be moved throughout the tumor with a pullback technique (distal, middle and proximal) if possible and be removed after each injection or when all tumors have been injected (see [Injection Manual](#) for more details).

6. STUDY POPULATION

See supplements for further details on population specifics for DEC, DEC2, FEC cohorts or potentially GEC cohort.

6.1. Inclusion Criteria

1. The participant (or legally acceptable representative if applicable) provides written informed consent for the trial.
2. Men and Women \geq 18 years of age on the day of signing consent.
3. Have an Eastern Cooperative Oncology Group (ECOG) performance status \leq 2; (**for pembrolizumab and ipilimumab combinations please see supplements DEC/DEC2 and FEC for ECOG criteria**).
4. Populations: INT230-6 will be injected into deep or superficial tumors for subjects with histologically or cytologically confirmed advanced or metastatic cancers; (**for pembrolizumab and ipilimumab combinations please see supplements DEC/DEC2 and FEC for Populations**).
5. Includes subjects with loco-regional disease that have relapsed/recurred within 6 months of chemo-radiation and who have no standard of care.
6. Subjects with metastatic disease who have failed one or more approved standard therapies, or have no alternate approved therapy available. Failure of all approved therapies that have a modest or marginal impact on survival is not required as long as the treating physician believes that treatment on study is appropriate for the subject and documents that the subject elects to defer the approved therapies.

Note: There is no limit on the number of prior therapies that a patient (subject) may have received prior to enrollment in any cohort.

7. Subjects must have measurable disease by iRECIST 1.1 criteria including one target tumor for injection by the local site investigator/radiology. Superficial tumors must have one tumor greater than or equal to 1.0 cm, deep tumors greater than or equal to 1.0 cm (as measured by caliper (for non-injected tumors only) or image guidance). Lesions situated in a previously irradiated area are considered measurable if progression has been demonstrated in such lesions.
8. Subjects must have a minimum of one injectable lesion as determined by the investigator (for superficial tumors) or radiologist (deep tumors).
9. Prior chemotherapy or immunotherapy (tumor vaccine, cytokine, or growth factor given to control the cancer: systemic or IT) must have been completed at least 4 weeks prior to dosing (with the exception of kinase inhibitors or other short half-life drugs, a 2 week washout is acceptable prior to treatment) and all adverse events have either returned to baseline or stabilized.

Note: Subjects who have received prior platinum therapy are eligible irrespective of their response.

10. Prior systemic radiation therapy (either IV, intrahepatic or oral) completed at least 4 weeks prior to study drug administration; **(for ipilimumab combination please see supplement FEC exclusion criteria).**
11. Prior focal radiotherapy completed at least 2 weeks prior to study drug administration.
12. Prior major treatment-related surgery completed at least 4 weeks prior to study drug administration.
13. No prior primary or metastatic brain or meningeal tumors unless clinically and radiographically stable as well as off steroid therapy for at least 2 months.
14. Life expectancy ≥ 8 weeks; **(for ipilimumab combination please see supplement FEC inclusion criteria).**
15. A female participant is eligible to participate if she is not pregnant, not breastfeeding, and at least one of the following conditions applies:
 - a. Not a woman of childbearing potential (WOCBP)
 - b. A WOCBP subject who may become pregnant or who are sexually active with a partner and who could become pregnant agrees to use an effective form of barrier contraception during the study and for at least 180 days in monotherapy; **(for pembrolizumab and ipilimumab combinations please see supplements DEC/DEC2 and FEC for pregnancy criteria).** (Male subjects must agree to use contraception and refrain from sperm donation during the study for 180 days after administration of study drug.)
16. Have adequate organ function as defined by the below screening laboratory values that must meet the following criteria:
 - a. WBC $\geq 2000/\mu\text{L}$ ($\geq 2 \times 10^9/\text{L}$).
 - b. Neutrophils $\geq 1000/\mu\text{L}$ ($\geq 1 \times 10^9/\text{L}$); **(for pembrolizumab and ipilimumab combinations please see supplements DEC/DEC2 and FEC for neutrophil criteria).**
 - c. **For subjects with planned superficial only injections:** PT, PTT/aPTT, and INR $\leq 1.5 \times \text{ULN}$, Platelets $\geq 70 \times 10^3/\mu\text{L}$ ($\geq 70 \times 10^9/\text{L}$), Hemoglobin $\geq 8 \text{ g/dL}$
 - d. Creatinine within the institution's laboratory upper limit of normal or calculated creatinine clearance $> 50 \text{ ml/min}$; **(for pembrolizumab combination please see supplements DEC/DEC2 for creatine criteria).**
 - e. ALT (SGOT)/AST (SGPT) $\leq 2.5 \times \text{ULN}$ without, and $\leq 5 \times \text{ULN}$ with hepatic metastases.
 - f. Bilirubin $\leq 2 \times \text{ULN}$ (except subjects with Gilbert's syndrome, who must have total bilirubin $< 3.0 \text{ mg/dL}$ ($< 52 \mu\text{mol/L}$)); **(for pembrolizumab and ipilimumab combinations please see supplements DEC/DEC2 and FEC for bilirubin criteria).**
 - g. **For subjects with planned deep tumor injections:** PT, PTT/aPPT, and INR within normal limits; Platelet count $\geq 100,000/\mu\text{L}$; hemoglobin $\geq 9 \text{ g/dL}$.

Note: ALT (SGPT) =alanine aminotransferase (serum glutamic pyruvic transaminase); AST (SGOT) =aspartate aminotransferase (serum glutamic oxaloacetic transaminase); ULN=upper limit of normal.

¹ Criteria must be met without erythropoietin dependency and without packed red blood cell (pRBC) transfusion within last 2 weeks.

17. Additional criteria for combination arms can be found in the appropriate supplements.

6.2. Exclusion Criteria

Subjects who exhibit any of the following conditions at Screening will not be eligible for admission into the study: **See DEC/DEC2, FEC, or potentially GEC supplements for additional criteria specific to those cohorts.**

18. History of severe hypersensitivity reactions to cisplatin or vinblastine or other products of the same class.
19. Other prior malignancy, except for adequately treated basal or squamous cell skin cancer or superficial bladder cancer, or any other cancer from which the subject has been disease-free for at least 2 years.
20. Subjects with tumors >15 cm (in longest diameter). Treatment plan for subjects with tumors that are 9 to 15 cm must be discussed with and approved by the medical monitor.
21. Underlying medical condition that, in the Principal Investigator's opinion, will make the administration of study drug hazardous or obscure the interpretation of toxicity determination or adverse events.
22. Concurrent medical condition requiring the use of immunosuppressive medications, or systemic corticosteroids (topical steroids are permitted); systemic corticosteroids must be discontinued at least 4 weeks prior to dosing. Inhaled or intranasal corticosteroids (with minimal systemic absorption) may be continued if the subject is on a stable dose. Non-absorbed intra-articular steroid injections will be permitted; or use of other investigational drugs (drugs not marketed for any indication) within 30 days prior to study drug administration. Use of steroids as prophylactic treatment for subjects with contrast allergies to diagnostic imaging contrast dyes will be permitted.
23. For deep tumor cohorts, subjects who require uninterrupted anticoagulants of any type, on daily aspirin therapy or NSAIAAs.
24. Use of other investigational drugs (drugs not marketed for any indication) within 28 days prior to study drug administration.

Pregnancy Exclusion:

A WOCBP who has a positive urine pregnancy test (e.g., within 72 hours) prior to treatment. If the urine test is positive or cannot be confirmed as negative, a serum pregnancy test will be required

NOTE: For specific inclusion/exclusion criteria relating to a potential combination, please refer to the combination specific supplement

7. ASSIGNMENT TO STUDY

The investigative site will contact Catalyst for treatment assignment once a subject is determined to be eligible for enrollment. Subjects who meet all eligibility requirements will be assigned to a treatment group as determined by Catalyst. Once assigned, numbers for screen failures, non-treated, non-evaluable, or discontinued subjects will not be re-used.

8. DOSAGE AND ADMINISTRATION

8.1. Investigational Product

An investigational product, also known as investigational medicinal product in some regions, is defined as follows: A pharmaceutical form of an active substance or placebo being tested or used as a reference in a clinical study, including products already with a marketing authorization but used or assembled (formulated or packaged) in a way different from the authorized form, or used for an unauthorized indication, or when used to gain further information about the authorized form. The investigational product should be stored in a secure area according to local regulations. It is the responsibility of the investigator to ensure that investigational product is only dispensed to study subjects. The investigational product must be dispensed only from official study sites by authorized personnel according to local regulations. In this protocol, investigational product(s) is: INT230-6, an anti-PD1 (pembrolizumab), CTLA-4 antibody (ipilimumab), or other drug.

8.2. Non-Investigational Product

Other medications used in the study as support or rescue medication for preventative, diagnostic, or therapeutic reasons, as components of the standard of care for a given diagnosis, are considered non-investigational products. In this protocol, non-investigational products are local anesthesia, anti-emetics (if prescribed by the investigator) and sedation.

8.3. Physical Description of Study Drug

INT230-6 is supplied in a frozen single use 10 mL or 30 mL amber vial. Each vial contains:

Name of Active Ingredients:

Cisplatin, (cis-diamminedichloroplatinum - CIS) 0.5mg/mL and

Vinblastine Sulfate (VBL) 0.1 mg/mL

Name of Important Excipients:

Sodium 2-hydroxybenzoylaminooctanoate (SHAO) 10 mg/mL (of free acid).

8.4. Packaging and Labeling

The study drug will be packaged and labeled according to current good manufacturing practices (GMP). Details of the packaging and labeling of clinical supplies may be found in the [Pharmacy and Drug Product Labeling Manual](#).

8.5. Ordering Study Drug

Clinical supplies may be requested by completing the Clinical Supplies Request Form and faxing it or e-mailing the form to the Sponsor with a copy to Catalyst.

8.6. Storage

Sterile INT230-6 has demonstrated that when stored frozen for 2 years at -20°C all three main ingredient substances comprising the drug product retain approximately ~100% of their T=0 concentrations upon thaw. Long term stability studies are in process.

Confirmation of the drug product's stability for use beyond 24 months shall be provided prior to use for drug product batches older than 24 months.

INT230-6 vials must be stored at a temperature of approximately -20°C (-15°C to -25°C is acceptable) and should be protected from light. Recommended safety measures for preparation and handling of INT230-6 include laboratory coats and gloves. After INT230-6 has been removed from the freezer, the total storage time (at room temperature) is not to exceed 4 hours.

Care must be taken to assure sterility of the prepared solution as the product does not contain any anti-microbial preservative or bacteriostatic agent.

The product storage manager should ensure that the study drug is stored in accordance with the environmental conditions (temperature, light, and humidity) as determined by the sponsor. If concerns regarding the quality or appearance of the study drug arise, do not dispense the study drug and contact the sponsor immediately.

8.7. Study Drug Preparation and Administration

INT230-6 is to be administered as an intratumoral injection. Each 10 mL or 30 mL vial of INT230-6 must be thawed to room temperature prior to use. (See [Injection and Dosing Manual Section 2.1](#) for determining the number of vials to thaw for each subject session for each cohort). Heating of the INT230-6 vials is not permitted. Thaw by placing the vials needed for dosing on a bench at room temperature. After one hour gently shake the vials to assure that any particulates that may be visible go into solution. INT230-6 must be dosed within 1 to 4 hours following removal from the freezer assuring that the vial is at room temperature at time of preparation. Injection of tumors must be performed under ultrasound, endoscopic or CT guidance. The extent of necrosis in the tumor should be assessed prior to re-injecting the same tumor.

If dosing into superficial tumors, prepare a standard syringe and sufficiently sized 22 gauge (or finer e.g. 23, 24 gauge) needle of proper length for the size of the tumor. (See below for dosing deep tumors). Remove the foil overseal from the vial and place the needle into the rubber stopper. Draw the appropriate drug volume for the tumor to be dosed into the syringe at either the 0.25 mL per cm³ of tumor or 0.5 mL per cm³ of tumor

ratio (depending on the cohort to be dosed). Use a fractionating technique to assure that the dose of INT230-6 is administered to each quadrant of the tumor. If known, dose into the proliferating portion of the tumor rather than into any necrotic areas. Administer the entire dose throughout the tumor (**moving the needle throughout the tumor as outlined per the [Injection Manual](#)**) gently pushing the plunger. Prior to withdrawing the needle from the tumor, count to 30 to assure time for the INT230-6 formulation to thoroughly diffuse throughout the tumor. If tumor is superficial with potential for ulceration (e.g. melanoma), please cover with an occlusive dressing which can be removed in 48 hrs.

For dosing into deep tumors note Sponsor shall provide a special syringe (see [PK and Biomarker Manual](#) and [Injection Manual](#) for further intratumoral deep tumor dosing information). **Note:** it takes approximately 1 mL to prime the tubing for the injection device.

Care must be taken to maintain the sterility of the INT230-6 solution as the product does not contain any anti-microbial preservative or bacteriostatic agents. Do not reinsert the needle into the vial after the subject has been dosed. Use a fresh, clean drawing needle if more material from the vial is to be used.

Anti-PD1 and anti CTLA4 therapy will be prepared as directed in the relevant Supplements

Training videos have been prepared by the Sponsor for:

25. Drug Preparation
26. Dosing Superficial Tumors
27. Deep Tumor Dosing

It is expected that research staff who are involved in any of the above activities (drug preparation, labelling or dosing) view the videos and that training is documented prior to involvement in such activities.

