This is a clinical study of a new investigational treatment that uses a novel drug product called "INT230-6" to treat advanced cancers. INT230-6 is a fixed ratio, multi-agent formulated drug product designed specifically for intratumoral (IT) injection. This study will determine the safety of administering a fixed volume of INT230-6 per cm³ of tumor into superficial, followed by multiple deep tumors. A sentinel subject will be enrolled at the lowest dose and followed for 4 weeks prior to escalating or adding additional subjects. Gradual intra-subject dose escalation will be done to increase the total amount of drug delivered to enable large tumors to be fully dosed at the proposed drug to tumor ratios. Once escalation dosing cohorts are complete, if no MTD is obtained, then set a fixed total dose of INT230-6 to be used for all dosings. Using fixed doses INT230-6 treatment shall consist of an induction phase for certain cohorts along with a maintenance regimen. INT230-6 will also be tested in combination with additional agents such as checkpoint antibodies in escalation or fixed dosing.

Dose escalation

There are 6 cohorts of subjects in the escalation portion of the protocol where INT230-6 dosing is increased over 5 doses. These escalation cohorts are (A, B1, EA, EC, EC2 and DEC). **Enrollment in these cohorts is closed.**

Cohort 1 (A) was a superficial tumor cohort starting at up to 5.0 mL of total dose with a low tumor load (1:4 ratio of drug to tumor).

Cohort 2 (B1) was a deep tumor cohort starting at up to 5.0 mL and escalates the total dose and maximal dose per any one tumor.

Cohort 3 (EA) explored administration in superficial tumors every 2 weeks.

Cohort 4 (EC) explored administration in both superficial and deep tumors every 2 weeks at a higher drug load (1:2 ratio) and will escalate the total dose and maximal dose per any one tumor.

Cohort 5 (EC2) explored administration in both superficial and tumors every 2 weeks at an intermediate drug load (1:3 ratio) and will escalate the total dose and maximal dose per any one tumor.

Cohort 6 (DEC) combined pembrolizumab and escalating doses of INT230-6 and includes a safety lead-in cohort that doses INT230-6 in superficial tumors.

Fixed Dose INT230-6

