There are 4 cohorts that use a maximum total fixed dose of INT230-6 of 175 mL for all 5 induction doses and along with maintenance doses. The maintenance dose is an INT230-6 dose given every 9 weeks +/- 10 days up to a maximum total dose amount of 175 mL. The fixed dose cohorts are EC3, DEC2, FEC and potentially GEC and each follows the Q2 week INT230-6 dosing schedule at drug load to tumor volume ratio of 1:3 into both superficial and deep tumors for tumor types defined in the appropriate supplement.

Cohort 7 (EC3) explores administration of INT230-6 monotherapy for any tumor type.

Cohort 8 (DEC2) combines a fixed dose of pembrolizumab with the same INT230-6 dosing regimen of EC3 as outlined in Supplement A.

Cohort 9 (FEC) combines a fixed dose of ipilimumab with the same INT230-6 dosing regimen of EC3 as outlined in Supplement A.

Future Cohort 10 (G cohort) combines INT230-6 with other molecules.

Additional cohorts can be added depending on review of safety data by the Study Steering Committee. All cohorts and decisions to escalate the dose and introduce new subject populations will be governed by the Study Steering Committee (SSC).

Expansion cohorts

The SSC reviewed the safety and any available biologic and/or tumor measurement data, a decision to open expansion cohorts of 10-16 subjects with a single tumor type was made. These groups will allow for better point estimates of the safety and preliminary efficacy in a homogenous population.

Number of subjects (planned):

The sample size (estimated to be between 100 and 175 subjects) during dose escalation cannot be precisely determined but depends on the observed toxicity. In expansion cohorts, up to 16 subjects will be treated at fixed doses in a tumor type, to provide preliminary assessment of tumor response, in addition to safety assessment.

Diagnosis and main criteria for inclusion:

Key Inclusion Criteria

1. The participant (or legally acceptable representative if applicable) provides written informed consent for the trial.
2. Men and Women ≥ 18 years of age on the day of signing consent.
3. Have an Eastern Cooperative Oncology Group (ECOG) performance status ≤ 2 ; (**for pembrolizumab and ipilimumab combinations please see supplements DEC/DEC2 and FEC for ECOG criteria**).
4. Populations: INT230-6 will be injected into deep or superficial tumors for subjects with histologically or cytologically confirmed advanced or metastatic cancers; (**for pembrolizumab**

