5.2. Fixed Dose

Cohorts (EC3, DEC2, FEC and potentially GEC) shall use a maximum fixed dose of INT230-6 of 175 mL per dosing session with the number of tumors being dosed per session to be decided by the investigators.

Based on preliminary data from the IT-01 study, the ratio of length to width to height is very consistent across the first 200+ tumors that we have volumetric based dosing using the modified ellipsoid formula. We have used this data to simplify the dosing based on the longest diameter measurement alone. The dose of INT230-6 will be calculated using the algorithm in Table 8.

Table 8: INT230-6 Dosing calculations

[REDACTED]	[REDACTED]	[REDACTED]	[REDACTED]	[REDACTED]
[REDACTED]	[REDACTED]	[REDACTED]	[REDACTED]	[REDACTED]
[REDACTED]				
[REDACTED]				
[REDACTED]				

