5.2.1. E. SUPERFICAL and/or DEEP TUMORS (cohort EC3) Monotherapy of INT230-6

This cohort has simplified the dosing to inject up to the 175mL total dose of INT230-6 into a subject's tumors at each treatment (5 total for induction) session. There is 1 mL of INT230-6 dosed for each 3 cc of tumor volume (1:3) ratio with an induction dosing of 1 doses every 2 weeks for 5 doses with maximum fixed total dose of 175 mL with a maintenance dose of the same maximum of 175 mL given Q9 weeks +/- 10 days. Each tumor should receive up to its

maximum dose to achieve the 1:3 target ratio. The total dose is to be divided up and injected into as many tumors as feasible, with the aim to treat as many visible tumors as possible 1 to 3 times during the course of the induction treatment. After the 5 doses, subjects continue to the maintenance phase where they can repeat injecting new lesions or previously injected lesions with up to 175mL once every 9 weeks. Treatment should continue until patient's tumors disappear (CR), confirmed progression (iCPD) or 2 years whichever is first.

5.2.2. DEC2 Cohorts. COMBINATION WITH ANTI-PD-1 agent(s): see Supplement A for details on each PD-1 agent.

DEC cohorts were initiated and are a combination of INT230-6 plus an anti-PD-1 therapy. The subject population (tumor types) and other details for this group of subjects is defined in Supplement A.

5.2.3. FEC Cohorts. COMBINATION WITH ANTI-CTLA4 agent(s): see Supplement B for protocol details for INT230-6 combinations with anti-CTLA-4 agent(s).

Cohort FEC was initiated and is a combination of INT230-6 plus an anti-CTLA4 therapy. The subject population (tumor types) and other details for this group of subjects is defined in Supplement B.

5.2.4. GEC Cohorts. Cohorts containing the letter “G” dose INT230-6 with agents other than PD-(L)1 or CTLA-4 antibodies.

The subject population (tumor types) and other details for this potential group of subjects will be defined in a future Supplement C.

Study Steering Committee

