10. COMPLIANCE

The Investigator or their designated study personnel will maintain a log of all study drugs received, dispensed, destroyed, and returned. Drug supplies will be inventoried and accounted for throughout the study.

The Investigator and the study personnel will ensure that each subject receives the calculated dose of the study drug based on tumor volume, as in section 5.2.

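### Protocol 8.7 still tells staff to draw drug for superficial tumors at 1:4 or 1:2, the ratios of closed cohorts; the fixed-dose cohorts are set at 1:3 through Table 8

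*Protocol*

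**What the plan says.** Section 8.7 is written as a set of steps for the person preparing the syringe. For superficial tumors it has the drug drawn "at either the 0.25 mL per cm³ of tumor or 0.5 mL per cm³ of tumor", the choice depending on the cohort. Its deep-tumor text gives no ratio and is not at issue.

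Other sections set a different rule for the cohorts that follow escalation:

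- Synopsis, on EC3, DEC2, FEC and potentially GEC: "each follows the Q2 week INT230-6 dosing schedule at drug load to tumor volume ratio of 1:3 into both superficial and deep tumors".
- Section 5.2.1, on EC3: "There is 1 mL of INT230-6 dosed for each 3 cc of tumor volume (1:3) ratio".
- Section 5.2, on the same four cohorts: they "shall use a maximum fixed dose of INT230-6 of 175 mL per dosing session". It adds: "The dose of INT230-6 will be calculated using the algorithm in Table 8".
- Section 5.5 asks investigators to "dose as many tumors as possible at least 2 or 3 times at the proper dose as noted in" Table 8.
- Section 10 requires site staff to "ensure that each subject receives the calculated dose of the study drug based on tumor volume, as in section 5.2".

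On the escalation cohorts (A, B1, EA, EC, EC2 and DEC), the Synopsis states: "Enrollment in these cohorts is closed".

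**The concern.** The drawing step offers two ratios and no third. Making the choice depend on the cohort does not help, because neither option belongs to EC3, DEC2, FEC or GEC. The basis of the calculation is out of date as well. Section 3.9 says Amendment 6 sets each tumor's dose from its longest diameter, while 8.7 still works per cm³ of tumor.

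The product contains cisplatin and vinblastine, so a wrong figure at the drawing step is a dosing matter. The lower ratio also has a cost. The SAP's research hypothesis (section 3.1) describes the optimal ratio as above 1 mL per 4 cc, and 0.25 mL per cm³ is exactly 1:4, so it does not exceed that.

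**Working it through.** **Inputs.** Ratios in 8.7: 0.25 and 0.5 mL per cm³. Cohort ratios: A1, B1 and EA 1:4, EC 1:2 and EC2 1:3 (Protocol 5.1); EC3, DEC2, FEC and potentially GEC 1:3 (Synopsis; 5.2.1 for EC3). SAP Table 3 also lists 1:3 for EC3, DEC2 and FEC. Session cap for the fixed-dose cohorts: 175 mL (5.2).

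**Where the figures in 8.7 come from.** 1/4 = 0.25 mL per cm³, which matches A1, B1 and EA. 1/2 = 0.50 mL per cm³, which matches EC. 1/3 = 0.333 mL per cm³ matches neither.

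**Size against the 1:3 target.**

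- 0.25 ÷ (1/3) = 0.75, or 25% below target.
- 0.50 ÷ (1/3) = 1.50, or 50% above target.

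**Example, one 30 cc superficial tumor.** Target 30/3 = 10 mL. Under 8.7: 30 × 0.25 = 7.5 mL, or 30 × 0.5 = 15 mL.

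**Effect of the session cap.** This assumes that everything injected in the session is superficial, since 8.7 gives no ratio for deep tumors. The cap is reached at 175/0.5 = 350 cc for 1:2, 175 × 3 = 525 cc for 1:3 and 175/0.25 = 700 cc for 1:4.

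| Total injected volume | 1:3 target | At 0.25 mL/cm³ | At 0.5 mL/cm³ |
|---|---|---|---|
| up to 350 cc | volume/3 | 75% | 150% |
| 400 cc | 133.3 mL | 100 mL (75%) | 175 mL, capped (131%) |
| 525 cc | 175 mL | 131.25 mL (75%) | 175 mL (100%) |
| 600 cc | 175 mL | 150 mL (86%) | 175 mL (100%) |
| 700 cc or more | 175 mL | 175 mL (100%) | 175 mL (100%) |

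**Overdose wording.** An excess of exactly 50% lies on the protocol's boundary. Section 13.4 sets the threshold at 50% or more, and the excess meets it if that is read as an excess over the intended dose. Section 13.2 requires more than 50% above the intended dose, and the excess does not meet that.

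**Limit of the check.** The cells of Table 8 are redacted in the public copy, so the volume it prescribes for a given diameter cannot be compared with 8.7. All percentages are against the 1:3 target stated in clear text.

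**The case against.** The strongest reply is that the governing rule is stated elsewhere in mandatory terms. Section 5.2 sends the fixed-dose calculation to Table 8, 5.5 refers to Table 8 again, and section 10 makes site staff responsible for the dose in 5.2. Section 8.7 assigns neither of its ratios to a fixed-dose cohort, so the error arises only if someone applies a closed cohort's ratio despite those sections. Section 8.7 also refers to injection manuals, and training videos on preparation and superficial dosing are required viewing; these may give the right volume. All of this stands, and it is why no misdosing is claimed. It does not make the instruction in 8.7 correct.

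Other points also have weight:

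- **Tolerability.** Cohort EC used 1:2 and section 5.1.4 reports no DLTs. But EC's session maximum was 120 mL, against 175 mL now, and tolerability does not make 1:2 the intended dose.
- **Timing.** SAP section 5 reports final enrollment of 110, so the correction would mainly serve any maintenance dosing still under way. The documents do not show how much remains.
- **Analysis.** Exposure is summarized from the dose administered (SAP 8.4), and the percentage of tumor burden dosed uses the cumulative dose (SAP Appendix 1). Neither calculation uses the ratio in 8.7.
- **Overdose.** The boundary result depends partly on a mismatch between 13.2 and 13.4, which is a separate matter.

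**Conclusion.** The concern holds. The superficial-tumor instruction in 8.7 gives only the 1:4 and 1:2 ratios of closed cohorts and is wrong for EC3, DEC2, FEC and any GEC. The discrepancy is 25% below or 50% above the stated 1:3 target and shrinks only in large-volume sessions where the 175 mL cap applies. The percentages rest on the clear-text 1:3 target, and the cap thresholds on a session confined to superficial tumors.

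This is an internal inconsistency in an operative dosing section. It changes no sample size, endpoint or analysis, and other sections reduce its practical risk. It should still be fixed, because it is a wrong figure at the drawing step for a cytotoxic product.

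**What to change.** In 8.7, have staff draw the volume given by Table 8 in section 5.2 (target 1:3, maximum 175 mL per session) for EC3, DEC2, FEC and any GEC. Keep 0.25 mL per cm³ only as the historical ratio of A1, B1 and EA, and 0.5 mL per cm³ only as that of EC. For a complete record the sentence can add that the closed cohorts EC2 (Protocol 5.1.4) and DEC (SAP Table 3) used 1:3. Check that the injection manuals agree.

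The cost is one sentence of protocol clarification, with no change to design, data collection or analysis.
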